3.3.3 Exclusion criteria

Subjects will not be allowed to participate, if any of the following general criteria apply:

1. Any finding in the medical examination (including BP, PR or ECG) deviating from normal and assessed as clinically relevant by the investigator
2. Repeated measurement of systolic blood pressure outside the range of 90 to 140 mmHg, diastolic blood pressure outside the range of 50 to 90 mmHg, or pulse rate outside the range of 45 to 90 bpm
3. Any laboratory value outside the reference range that the investigator considers to be of clinical relevance
4. Any evidence of a concomitant disease assessed as clinically relevant by the investigator
5. Gastrointestinal, hepatic, renal, respiratory, cardiovascular, metabolic, immunological or hormonal disorders
6. Cholecystectomy or other surgery of the gastrointestinal tract that could interfere with the pharmacokinetics of the trial medication (except appendectomy or simple hernia repair)
7. Diseases of the central nervous system (including but not limited to any kind of seizures or stroke), and other relevant neurological or psychiatric disorders
8. History of relevant orthostatic hypotension, fainting spells, or blackouts
9. Relevant chronic or acute infections
10. History of relevant allergy or hypersensitivity (including allergy to the trial medication or its excipients, including also peanut and soy)
11. Use of drugs within 30 days of planned administration of trial medication that might reasonably influence the results of the trial (including drugs that cause QT/QTc interval prolongation) or any (re-)vaccination within 30 days before first trial medication or planned during the trial
12. Intake of an investigational drug in another clinical trial within 60 days of planned administration of investigational drug in the current trial, or concurrent participation in another clinical trial in which investigational drug is administered
13. Smoker (more than 10 cigarettes or 3 cigars or 3 pipes per day)
14. Inability to refrain from smoking on specified trial days
15. Alcohol abuse (consumption of more than 24 g per day)
16. Drug abuse or positive drug screening
17. Blood donation of more than 100 mL within 30 days of planned administration of trial medication or intended blood donation during the trial

Proprietary confidential information © 2021 Boehringer Ingelheim International GmbH or one or more of its affiliated companies

18. Intention to perform excessive physical activities within one week prior to the administration of trial medication or during the trial
19. Inability to comply with the dietary regimen of the trial site
20. Subject is assessed as unsuitable for inclusion by the investigator, for instance, because the subject is not considered able to understand and comply with study requirements, or has a condition that would not allow safe participation in the study
21. Body weight lower than 65 kg
22. Increased bleeding risk, including known genetic predisposition to bleeding, use of medication that could relevantly increase bleeding risk (e.g. low-molecular weight heparin; recent use of non-steroidal anti-inflammatory drugs is allowed), history of haemorrhagic central nervous system event within 12 months of planned first study medication, or any of the following within 3 months of planned first study medication: Haemoptysis or macrohaematuria, active gastro-intestinal bleeding or gastro-intestinal ulcers, or major injury or surgery (investigator judgement)
23. During Covid-19 pandemic: laboratory test indicative of an ongoing SARS-CoV-2 infection

For study restrictions, refer to Section [4.2.2](#).

3.3.4 Withdrawal of subjects from treatment or assessments

Subjects may discontinue trial treatment or withdraw consent to trial participation as a whole ('withdrawal of consent') with very different implications; please see Sections 3.3.4.1 and [3.3.4.2](#) below.

If a subject is removed from or withdraws from the trial prior to the first administration of trial medication, the data of this subject will not be entered in the case report form (CRF) and will not be reported in the clinical trial report (CTR). If a subject is removed from or withdraws from the trial after the first administration of trial medication, this will be documented and the reason for discontinuation must be recorded in the CRF; in addition, the data will be included in the CRF and will be reported in the CTR. At the time of discontinuation, a complete end of trial examination will be performed, if possible, and the information will be recorded in the CRF. If the discontinuation occurs before the end of the REP (see Section [1.2.1](#)), the discontinued subject should if possible be questioned for AEs and concomitant therapies at or after the end of the REP in order to ensure collection of AEs and concomitant therapies throughout the REP, if not contrary to any consent withdrawal of the subject.

3.3.4.1 Discontinuation of trial treatment

An individual subject will discontinue trial treatment if:

1. The subject wants to discontinue trial treatment, without the need to justify the decision
2. The subject has repeatedly shown to be non-compliant with important trial procedures and, in the opinion of both, the investigator and sponsor representative, is not willing or able to adhere to the trial requirements in the future.

Proprietary confidential information © 2021 Boehringer Ingelheim International GmbH or one or more of its affiliated companies

3. The subject needs to take concomitant medication that interferes with the investigational medicinal product or other trial treatment
4. The subject can no longer receive trial treatment for medical reasons (such as surgery, adverse events [AEs], or diseases)
5. The subject has an elevation of AST and/or ALT ≥ 3 -fold ULN and an elevation of total bilirubin ≥ 2 -fold ULN (measured in the same blood sample) and/or needs to be followed up according to the DILI checklist provided in the ISF
6. An AE or clinically significant laboratory change or abnormality occurs that the investigator assesses as warranting discontinuation of treatment. This may include:
 - The subject has an elevation of AST and/or ALT ≥ 3 -fold ULN

In addition to these criteria, the investigator may discontinue subjects at any time based on his or her clinical judgment.

Even if the trial treatment is discontinued, the subject remains in the trial and, given his/her agreement, will undergo the procedures for early treatment discontinuation and follow up as outlined in the [Flow Chart](#) and section [6.2.3](#).

3.3.4.2 Withdrawal of consent to trial participation

Subjects may withdraw their consent to trial participation at any time without the need to justify the decision. If a subject wants to withdraw consent, the investigator should be involved in the discussion with the subject and explain the difference between trial treatment discontinuation and withdrawal of consent to trial participation, as well as explain the options for continued follow up after trial treatment discontinuation, please see Section [3.3.4.1](#) above

3.3.4.3 Discontinuation of the trial by the sponsor

Boehringer Ingelheim reserves the right to discontinue the trial at any time for any of the following reasons:

1. Failure to meet expected enrolment goals overall or at a particular trial site
2. New toxicological findings, serious adverse events, or any safety information invalidating the earlier positive benefit-risk-assessment. More specifically, the trial will be terminated if more than 50% of the subjects have drug-related and clinically relevant adverse events of moderate or severe intensity, or if at least 1 drug-related serious adverse event is reported
3. Violation of GCP or the CTP impairing the appropriate conduct of the trial
4. The sponsor decides to discontinue the further development of the investigational product

3.3.5 Replacement of subjects

In case more than 2 subjects do not complete the trial (including non PK evaluable subjects), the CT Leader together with the Trial Pharmacokineticist and the Trial Statistician are to decide, if and how many subjects will be replaced. A replacement subject will be assigned a unique trial subject number, and will be assigned to the same treatment as the subject he or she replaces.

4. TREATMENTS

4.1 INVESTIGATIONAL TREATMENTS

The investigational products will be supplied by BI Pharma GmbH & Co. KG.

4.1.1 Identity of the Investigational Medicinal Products

The characteristics of the test product are given below:

Substance: Nintedanib
Pharmaceutical formulation: Soft gelatin capsule
Source: BI Pharma GmbH & Co. KG, Germany
Unit strength: 25 mg
Posology: 4-0-0
Route of administration: oral
Duration of use: One single dose

The characteristics of the reference product are given below:

Substance: Nintedanib
Pharmaceutical formulation: Soft gelatin capsule
Source: BI Pharma GmbH & Co. KG, Germany
Unit strength: 100 mg
Posology: 1-0-0
Route of administration: oral
Duration of use: One single dose

4.1.2 Selection of doses in the trial

The doses selected for this trial are suitable to assess PK of 4 capsules à 25 mg nintedanib in comparison to one capsule à 100 mg nintedanib.

4.1.3 Method of assigning subjects to treatment groups

The randomisation list will be provided to the trial site in advance.

According to the planned sample size, 2 cohorts are planned. Prior to the start of the study, subjects willing to participate will be recruited to cohorts according to their temporal availability. In the morning of Day 1 (Visit 2), subjects will be allocated to treatment sequences prior to the first administration of trial medication. For this purpose, numbers of the randomisation list will be allocated to the subjects by drawing lots. Subjects are then assigned to a treatment sequence according to the randomisation list.

Once a subject number has been assigned, it cannot be reassigned to any other subject.

The randomisation procedure is described in Section [7.6](#).

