6.2.2 Treatment periods

Each subject is expected to participate in 2 treatment periods (Days 1, 2, 3, and 4 in each period). At least 7 days will separate drug administrations in the first and second treatment periods.

On Day 1 of each treatment period, study participants will be admitted to the trial site and kept under close medical surveillance for at least 24 h following drug administration. The subjects will then be allowed to leave the trial site after formal assessment and confirmation of their fitness. On all other study days, subjects will be treated in an ambulatory fashion.

Proprietary confidential information © 2021 Boehringer Ingelheim International GmbH or one or more of its affiliated companies

For details on time points and procedures for collection of plasma samples for PK analysis, refer to [Flow Chart](#) and Section [5.3.2](#).

The safety measurements performed during the treatment period are specified in Section [5.2](#) of this protocol and in the Flow Chart. For details on times of all other trial procedures, refer to the Flow Chart. AEs and concomitant therapy will be assessed continuously from screening until the end of trial examination.

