7.3.1 Primary endpoint analyses

Primary analyses

The statistical model used for the analysis of the primary endpoints will be an analysis of variance (ANOVA) model on the logarithmic scale. That is, the PK endpoints will be log-transformed (natural logarithm) prior to fitting the ANOVA model. This model will include effects accounting for the following sources of variation: sequence, subjects within sequences, period and treatment. The effect 'subjects within sequences' will be considered as random, whereas the other effects will be considered as fixed. The model is described by the following equation:

$$y_{ijkm} = \mu + \zeta_j + s_{im} + \pi_j + \tau_k + e_{ijkm}, \text{ where}$$

y_{ijkm} = logarithm of response measured on subject m in sequence i receiving treatment k in period j,

Proprietary confidential information © 2021 Boehringer Ingelheim International GmbH or one or more of its affiliated companies

μ = the overall mean,

ζ_i = the i^{th} sequence effect, $i = 1, 2$,

s_{im} = the effect associated with the m^{th} subject in the i^{th} sequence,
 $m = 1, 2, \dots, 20$

π_j = the j^{th} period effect, $j = 1, 2$,

τ_k = the k^{th} treatment effect, $k = 1, 2$,

e_{ijkm} = the random error associated with the m^{th} subject in sequence i who received treatment k in period j .

where $s_{im} \sim N(0, \sigma_B^2)$ i.i.d., $e_{ijkm} \sim N(0, \sigma_W^2)$ i.i.d. and s_{im} , e_{ijkm} are independent random variables.

Point estimates for the ratios of the geometric means (test/reference) for the primary endpoints (see Section [2.1](#)) and their two-sided 90% confidence intervals (CIs) will be provided.

For each endpoint, the difference between the expected means for $\log(T)-\log(R)$ will be estimated by the difference in the corresponding adjusted means (Least Squares Means). Additionally their two-sided 90% confidence intervals will be calculated based on the residual error from the ANOVA and quantiles from the t-distribution. These quantities will then be back-transformed to the original scale to provide the point estimate and 90% CIs for each endpoint.

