7.7 DETERMINATION OF SAMPLE SIZE

The sample size determination is not based on a power calculation, but assures a precise estimation of the relative bioavailability. For this trial a precision of 1.25 has been considered necessary and sufficient by the project team. Thereby, precision is defined as ratio of upper confidence interval limit to the relative BA estimate.

The observed intra-individual coefficient of variation (gCV) for nintedanib in previous trials [[c09412738-01](#)] was roughly 27% for C_{max} and 12% for AUC_{0-tz} .

Assuming an intra-individual variability of 30% for nintedanib, the trial will need 18 subjects in order to achieve two-sided 90% confidence intervals that have a precision of at least 1.25 with a probability of 95%. As an example, for the above stated assumptions and an expected ratio of geometric means (T/R) of 1.00, the expected two-sided 90% confidence interval will range from (0.80, 1.25).

Accounting for up to 2 non PK evaluable subjects, a total of $N = 18+2 = 20$ subjects are planned to be entered into the trial.

The calculation was performed as described by Julius [[R11-5230](#), Chapter 8] using R Version 4.0.2.

8. INFORMED CONSENT, TRIAL RECORDS, DATA PROTECTION, PUBLICATION POLICY, AND ADMINISTRATIVE STRUCTURE

The trial will be carried out in compliance with the protocol, the ethical principles laid down in the Declaration of Helsinki, in accordance with the ICH Harmonized Guideline for Good Clinical Practice (GCP), relevant BI Standard Operating Procedures (SOPs), the EU regulation 536/2014, and other relevant regulations. Investigators and site staff must adhere to these principles.

Standard medical care (prophylactic, diagnostic, and therapeutic procedures) remains the responsibility of the subject's treating physician.

The investigator will inform the sponsor immediately of any urgent safety measures taken to protect the trial subjects against any immediate hazard, as well as of any serious breaches of the protocol or of ICH GCP.

The Boehringer Ingelheim transparency and publication policy can be found on the following web page: trials.boehringer-ingelheim.com. As a general rule, no trial results should be published prior to archiving of the CTR.

The terms and conditions of the insurance coverage are made available to the investigator and the subjects, and are stored in the ISF.

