## 6.5 POOLING OF CENTRES

This section is not applicable, because the study was performed in only one centre.

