#### **7.4.1 Primary analysis of the primary endpoints**

##### **Section 7.3.1 of the CTP:**

*The statistical model used for the analysis of the primary endpoints will be an analysis of variance (ANOVA) model on the logarithmic scale. That is, the PK endpoints will be log-transformed (natural logarithm) prior to fitting the ANOVA model. This model will include effects accounting for the following sources of variation: sequence, subjects within sequences, period and treatment. The effect 'subjects within sequences' will be considered as random, whereas the other effects will be considered as fixed. The model is described by the following equation:*

$y_{ijkm} = \mu + \zeta_i + s_{im} + \pi_j + \tau_k + e_{ijkm}$ , where  
 $y_{ijkm}$  = logarithm of response measured on subject  $m$  in sequence  $i$  receiving treatment  $k$  in period  $j$ ,  
 $\mu$  = the overall mean,  
 $\zeta_i$  = the  $i^{th}$  sequence effect,  $i = 1, 2$ ,  
 $s_{im}$  = the effect associated with the  $m^{th}$  subject in the  $i^{th}$  sequence,  $m = 1, 2, \dots, 20$   
 $\pi_j$  = the  $j^{th}$  period effect,  $j = 1, 2$ ,  
 $\tau_k$  = the  $k^{th}$  treatment effect,  $k = 1, 2$ ,  
 $e_{ijkm}$  = the random error associated with the  $m^{th}$  subject in sequence  $i$  who received treatment  $k$  in period  $j$ .

where  $s_{im} \sim N(0, \sigma_B^2)$  i.i.d.,  $e_{ijkm} \sim N(0, \sigma_W^2)$  i.i.d. and  $s_{im}$ ,  $e_{ijkm}$  are independent random variables.

*Point estimates for the ratios of the geometric means (test/reference) for the primary endpoints (see CTP Section 2.1) and their two-sided 90% confidence intervals (CIs) will be provided.*

*For each endpoint, the difference between the expected means for log(T)-log(R) will be estimated by the difference in the corresponding adjusted means (Least Squares Means). Additionally their two-sided 90% confidence intervals will be calculated based on the residual error from the ANOVA and quantiles from the t-distribution. These quantities will then be back-transformed to the original scale to provide the point estimate and 90% CIs for each endpoint.*

The implementation for this analysis will be accomplished by using the CSD macros based on PKS. The following SAS code can be used:

```
PROC MIXED DATA=indata METHOD=REML;
  CLASS subject treatment sequence period;
  MODEL logpk = treatment sequence period / DDFM=KR;
  RANDOM subject(sequence);
  LSMEANS treatment / PDIFF CL ALPHA=0.1;
RUN;
```

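### Does running the trial in two cohorts mean that the primary model needs a cohort-specific period effect?

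*Protocol*

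**What the plan says.** Protocol 4.1.3 says "According to the planned sample size, 2 cohorts are planned", and then how they are filled: "Prior to the start of the study, subjects willing to participate will be recruited to cohorts according to their temporal availability". Sequences are drawn by lot on the morning of Day 1, after cohort membership is settled. Protocol 6.2.2 sets only a minimum spacing: "At least 7 days will separate drug administrations in the first and second treatment periods".

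For the primary endpoints, Protocol 7.3.1 says "This model will include effects accounting for the following sources of variation: sequence, subjects within sequences, period and treatment". The code in SAP 7.4.1 matches it: "MODEL logpk = treatment sequence period / DDFM=KR". Neither visible text has a cohort term.

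The sample size in Protocol 7.7 rests on interval width: "For this trial a precision of 1.25 has been considered necessary and sufficient by the project team". It continues: "Assuming an intra-individual variability of 30% for nintedanib, the trial will need 18 subjects in order to achieve two-sided 90% confidence intervals", with that precision to be reached with a probability of 95%. Two further subjects are added, giving 20. Protocol 7.2 sets no hypothesis test and no acceptance range. On centres, SAP 6.5 says: "This section is not applicable, because the study was performed in only one centre".

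**The concern.** Cohorts recruited by availability will probably be dosed on different dates, although no dates are given. Period 1 in one cohort may then not be the same occasion as Period 1 in the other. A model with one period effect assumes that the Period 1 to Period 2 change is the same in both. If it is not, the excess goes into the residual error from which the interval is calculated. The trial was sized on interval width alone, so the widening would fall on the very quantity the plan undertakes to control. If the sequences also happened to be uneven within cohorts, the realised T/R estimate would be displaced.

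**Working it through.** **Inputs.** From Protocol 7.7: planning CV 30%; observed CVs 27% (Cmax) and 12% (AUC0-tz); precision limit 1.25, so ln 1.25 = 0.2231; required probability 95%; 18 evaluable subjects, 20 entered. From Protocol 7.3.1: a 90% interval from the residual error and the t-distribution. Assumed, because the documents do not give them: two cohorts of equal size, and δ, the cohort difference in the log Period 1 to Period 2 change, taken from 0 to 0.2 (a ratio of 1.00 to 1.22).

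**1. The plan's own figure.** σ² = ln(1 + 0.30²) = 0.0862, so σ = 0.2936. With df = n − 2, the half-width is t × σ × √(2/n). At n = 18 this is 1.746 × 0.2936 × 0.3333 = 0.171, a precision of 1.186. The probability of meeting 1.25 is P(χ²₁₆ ≤ 16 × [0.2231/(1.746 × 0.3333)]²/0.0862) = P(χ²₁₆ ≤ 27.3) = 0.962. At n = 17 it is 0.934. The smallest n reaching 95% is therefore 18, as stated. At n = 20 it is 0.989.

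**2. What one period effect leaves out.** Take D, log Period 1 minus log Period 2, for each subject; its variance is 2σ². Subject effects, and any cohort difference that is constant over both periods, drop out of D. A cohort-specific shift puts the two cohort means of D at ±δ/2. With sequences balanced within cohort, the log T/R estimate does not move. The residual sum of squares gains n(δ/2)², which is a non-centrality of λ = n(δ/2)²/(2σ²). The half-width grows by about √(1 + λ/df).

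Example at n = 20, CV 30%, δ = 0.2: λ = 0.2/0.1724 = 1.16; √(1 + 1.16/18) = 1.032; precision moves from 1.175 to 1.181.

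**3. The planned model against its target.** N = 20 is split 5/5 in each cohort; n = 18 is split 5/4 and 4/5.

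| CV | δ | Precision, N = 20 | P(≤ 1.25), N = 20 | P(≤ 1.25), n = 18 |
|---|---|---|---|---|
| 30% | 0 | 1.175 | 0.989 | 0.962 |
| 30% | 0.1 | 1.176 | 0.988 | 0.957 |
| 30% | 0.2 | 1.181 | 0.981 | 0.941 |
| 27% | 0.2 | 1.163 | 0.997 | 0.987 |
| 12% | 0 | 1.068 | 1.00 | 1.00 |
| 12% | 0.2 | 1.080 | 1.00 | 1.00 |

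At CV 30% the 95% probability is lost above δ = 0.36 with 20 evaluable subjects, and above δ = 0.154 with 18. For AUC0-tz the interval is about 18% wider at δ = 0.2 in relative terms, but its precision of 1.080 is still far inside 1.25.

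**4. Bias and coverage.** Cohort membership is settled before the lots are drawn, so it is independent of sequence. Simulating a random 10:10 allocation with δ = 0.2 gave a mean log error of 0.000 and coverage of 90.2%, 90.1% and 90.0% at CVs of 12%, 27% and 30%.

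**5. What a period-within-cohort term would do.** It removes δ but costs one residual degree of freedom, and more if sequences are uneven within cohorts. At CV 30% with no shift:

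| Sequence split by cohort | Planned model | With the term |
|---|---|---|
| N = 20, 5/5 and 5/5 | 0.989 | 0.987 |
| n = 18, 5/4 and 4/5 | 0.962 | 0.951 |
| N = 20, 6/4 and 4/6 | 0.989 | 0.981 |
| N = 20, 7/3 and 3/7 | 0.989 | 0.946 |

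The term narrows the interval only above a break-even δ. At N = 20 (5/5) that is 0.063 for CV 30% and 0.026 for CV 12%. At n = 18 it is 0.114 and 0.046. At 7/3 and CV 30%, the interval with the term is wider at every δ up to 0.2.

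**The case for a change.** The best case for the term is this. Eighteen evaluable subjects is a situation the protocol allows for, and there the margin over 95% is only 1.2 points. A shift of 0.2 takes the planned model to 0.941, while the term holds 0.951 whatever the shift. Balance within cohort is not stated, and the block size is left to the trial report. At 7/3 and 3/7 with a shift of 0.2, the planned estimate is displaced by log 0.04, and coverage at CV 12% is 81%, against 90% with the term. The change costs one model line, and in an open-label trial a rule fixed in advance is better than one chosen afterwards.

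The facts and figures stand, but they do not amount to a fault. Losing the 95% probability needs three things together: a CV of 30%, above both observed values; both spare subjects lost; and a shift above 0.154. At the observed Cmax CV of 27%, 18 subjects and a shift of 0.2 still give 0.987. Nothing in the documents suggests such a shift, and one centre, identical periods and standardised meals make a large one less likely. Different dates alone do not create it.

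The 81% needs a 7/3 split, CV 12% and a shift of 0.2 together. At 6/4, coverage is 91%. In that same 7/3 split at CV 30%, the term itself misses the precision target (0.946). A sensitivity analysis with the term would do no harm, but it would not alter the primary result. Parts of the SAP after 7.4.1 are not visible, so its absence cannot be asserted.

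**Conclusion.** The concern does not hold. The plan does run two cohorts and does fit one period effect, but that model is coherent for a two-period crossover and agrees between protocol and SAP. It gives an unbiased T/R over the randomisation, with coverage near 90%. At the planned 20 subjects with balanced cohorts and CV 30%, the 1.25 precision target keeps its 95% probability up to an assumed log shift of about 0.36 (a ratio of 1.43).

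A cohort-specific period term trades a small certain cost for a gain that depends on a shift whose size nobody can state. The trial is estimation only, with no acceptance range, so no planned decision depends on the choice. Preferring the term is an analyst's option, and leaving it out is not an error.

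This rests on cohorts of equal size and on an assumed range for the shift; the documents give neither.
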